## 7.2 General Methodology

A comprehensive analysis of the pilot study results, as a whole, will be assessed to evaluate the overall risk/benefit balance for the patient population being treated. Pre-defined statistical “success” or “pass” criteria for the study endpoints are not applicable for this pilot study, as it is not a powered, hypothesis-driven study.

Each subject’s data will be reviewed individually and case summaries for all subjects will be provided to the FDA. In addition, descriptive statistics will be used to summarize the preoperative, operative, discharge, and follow-up clinical data. No statistical hypothesis tests are planned. The endpoint measures will be summarized by time point. Additionally, change from baseline will be presented for each outcome, as applicable.

To report the distributions of continuous variables, mean, standard deviation, minimum, median, first and third quartiles, and maximum will be presented. To report the distributions of categorical variables, counts and proportions will be provided. Proportions and associated 95% confidence intervals will be reported for endpoints, as applicable. For time to event data, Kaplan-Meier event rates will be presented at clinically meaningful post-operative time intervals, for instance, 30 days, 183 days, and annually thereafter (e.g., 365, 365×2, 365×3 days, etc.). At each time point with data, the product-limit estimate of the event rate, the number of subjects at risk, the number of subjects with events, the Greenwood standard error of the estimate, and the loglog transformed 95% confidence interval using the Greenwood standard error will be presented.

For subjects without an event, the date of censoring will be the latest date of all follow-up visits (including video contact, phone and/or mail correspondence), assessments, events (including death in those endpoints where death is not the endpoint) and study exits. For subjects whose exit reason is lost to follow-up, the last follow-up date will be the latest date of the follow-up visits (including video contact, phone and/or mail correspondence), assessments and events.

For analyses reporting the function of the study valve using echocardiographic or MDCT data, only data corresponding to the implanted study valve will be used; data post-explant or after reintervention in which the index study valve is no longer functioning will be excluded from the analysis.

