## 3. Introduction

Mitral regurgitation (MR) affects millions of people worldwide. It is the most common type of heart valve defect, affecting one in 10 people aged 75 and older. The condition occurs when the heart's mitral valve does not close completely, causing blood to leak backward into the left atrium with every heartbeat. Over time, left ventricular dilatation and dysfunction occurs in an attempt to accommodate the increased volume load and maintain cardiac output. Ultimately, chronic volume overloading of the left ventricle results in contractile dysfunction, symptoms of heart failure, and an increased risk of sudden death. Patients with severe symptomatic MR have a poor prognosis with an annual mortality rate of 5% per year without surgical intervention. Progressive heart failure is the usual cause of death, but patients also may die from sudden death, stroke, and endocarditis.

The investigational device is called the Intrepid™ Transcatheter Mitral Valve Replacement (TMVR) System, manufactured by Medtronic (formerly Twelve, Inc.). It is designed for trans-apical access and delivery of a self-expanding bioprosthetic valve within the native mitral valve. The Intrepid™ TMVR implant is intended to function similarly to a standard bioprosthetic valve implant, in that it allows blood to flow only in the forward direction, thereby relieving mitral regurgitation. A standard valve implant, however, is sewn directly into the heart during surgery in which the chest is fully open, the patient is put on cardiopulmonary bypass support and the heart is temporarily stopped. The Intrepid™ TMVR implant is intended to be placed through a less invasive mini-thoracotomy procedure, without requiring cardiopulmonary bypass support or stopping the heart, thereby reducing the risks associated with these more invasive procedures. The concept of the Intrepid™ TMVR System for mitral valve disease is similar to the concept of currently approved systems for standard trans-apical Transcatheter Aortic Valve Implantation (TAVI) systems for aortic valve disease.

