## 5. Investigation Plan

The study is a prospective, multi-center, non-randomized study to evaluate the safety and performance of The Intrepid™ TMVR System in patients with severe, symptomatic mitral regurgitation, who are at high risk for conventional mitral valve surgery.

The pilot study (also referenced as early feasibility study) is a single arm study without concurrent controls. The results will be evaluated referencing historical literature for surgical mitral replacement, surgical mitral repair, and transcatheter mitral repair.

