## 6. Determination of Sample Size

This study treats up to 95 subjects worldwide who require replacement of their native mitral valve because of severe, symptomatic mitral regurgitation, but are at high risk for conventional mitral valve surgery. The enrollment is capped at 70 in the US, 30 in Australia, and 20 in each of France, Denmark, Finland, Greece, and the UK. The geography-specific and overall sample sizes are not statistically derived, as this is not a hypothesis-driven study.

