## **7.8 Interim Analyses**

Interim analyses are planned for publication when 50 subjects had the opportunity to be followed for 30 days and a second analysis for CE submission when 75 subjects had the opportunity to be followed for 30 days. The final analysis and report will be completed when all enrolled subjects have completed the 5-year follow-up.

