## Endpoint Definition/Parameters to Be Estimated:

This endpoint is defined using the CEC adjudication for re-hospitalization for heart failure on the AE CRF.

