## Analysis Method:

This endpoint will be summarized using descriptive statistics for time to event data described in **Section 7.2**. Kaplan-Meier event rates at 30 days, 6 months, 12 months, and every 6 months through 5 years.

- MVARC defined technical success

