## 7.10 Safety Evaluation

The CEC will adjudicate all deaths, SAEs, and safety endpoint events reported by the investigators. The analysis of the study safety data will be based on CEC-adjudicated events. AE summaries will be based on MedDRA coding.

To provide a comprehensive safety evaluation, the safety data will be presented at aggregate and individual event levels as tables and listings. The safety data will be summarized by severity, time point, treatment needed, resolution, and causal relationship with the investigational devices or procedure using descriptive statistics for categorical variable described in **Section 7.2**. Any Unanticipated Adverse Device Effects (UADEs) will be reported as proportions of subjects experiencing the event. Time to event data will be reported using the Kaplan-Meier estimate of the event rate, the number of subjects at risk, the number of subjects with events, the Greenwood standard error of the estimate, and the loglog transformed 95% confidence interval using the Greenwood standard error, as described in **Section 7.2**.

A listing will be provided for:

- Deaths and reasons for death
- AEs related to the implant, delivery system, or procedure

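### The Pilot SAP reports heart failure re-hospitalization through 5 years as a death-censored Kaplan-Meier rate, which overstates the proportion of treated subjects with the event at late time points

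*Combined protocol and SAP*

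**What the plan says.** The SAP supplied is for the transapical Pilot Study (CIP-1403). Section 7.2 sets the censoring date for a subject without an event as the latest of follow-up contacts, assessments, study exit and "events (including death in those endpoints where death is not the endpoint". A subject who dies without the event in question is therefore censored at death. Section 7.4 censors drop-outs at discontinuation.

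Section 7.9.3 applies this to heart failure re-hospitalization in the Attempted Subjects set. On the definition: "This endpoint is defined using the CEC adjudication for re-hospitalization for heart failure on the AE CRF". Death is not a component. On the analysis: "Kaplan-Meier event rates at 30 days, 6 months, 12 months, and every 6 months through 5 years". Section 7.2 adds numbers at risk, numbers with events, the Greenwood standard error and a log-log 95% interval.

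Section 7.10 uses the same estimator for other safety outcomes: "Time to event data will be reported using the Kaplan-Meier estimate of the event rate". It also calls for a listing of deaths. Nowhere does the SAP specify a cumulative incidence function, a competing-risk method, or a composite with death.

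On use of the results, section 7.8 says "The final analysis and report will be completed when all enrolled subjects have completed the 5-year follow-up", and section 5 says "The results will be evaluated referencing historical literature for surgical mitral replacement, surgical mitral repair, and transcatheter mitral repair".

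**The concern.** A subject who has died can no longer be re-hospitalized. Censoring at death treats that subject as still able to have the event later, at the same rate as those still under observation. The resulting figure describes a hypothetical population without deaths. It can never be below the cumulative incidence, and it is above it as soon as a death is followed by a later event in someone else.

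A 5-year event rate with a 95% interval will naturally be read as the share of treated patients re-hospitalized for heart failure. It will be compared with published results and will enter the overall risk/benefit assessment. In a purely descriptive study the estimate and its interval are the result, so it matters that they describe the intended quantity. The overstatement makes the device look worse on this endpoint, so the correction is not against the sponsor's interest.

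**Working it through.** The SAP states no expected rate, event count or precision for this endpoint, so there is no planned figure to reproduce.

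**Inputs**
- Sample size: "This study treats up to 95 subjects worldwide" (SAP section 6). The US cap of 70 is a second case, since section 7.9.3 notes that the exploratory endpoints are listed only in the US and French CIPs.
- Mortality, low: "annual mortality rate of 5% per year without surgical intervention" (SAP section 3). Hazard λ = −ln(0.95) = 0.0513 per year, or 1 − 0.95⁵ = 22.6% dead at 5 years.
- Mortality, high: up to 50% at 5 years (section 3.1 of the separate transseptal Early Feasibility CIP). λ = −ln(0.5)/5 = 0.1386 per year.
- Both mortality figures are for unoperated patients. Neither document gives a rate for treated subjects.
- First heart failure re-hospitalization: hazard h = 0.10, 0.15 or 0.25 per year. This is an assumption; the documents give no post-implant rate.

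**Formulas** (constant hazards, independent times, all-cause mortality standing in for death without a prior re-hospitalization)
- Death-censored Kaplan-Meier targets 1 − exp(−ht).
- The proportion of treated subjects with the event is h/(h+λ) × [1 − exp(−(h+λ)t)].

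Example, h = 0.15, t = 5:
- Kaplan-Meier: 1 − exp(−0.75) = 52.8%.
- Cumulative incidence, λ = 0.0513: 0.15/0.2013 × [1 − exp(−1.0065)] = 47.3%.
- Cumulative incidence, λ = 0.1386: 0.15/0.2886 × [1 − exp(−1.443)] = 39.7%.

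**Five-year figures (%)**

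| h per year | Kaplan-Meier | Cumulative incidence, 5%/year | Gap | Cumulative incidence, 50% at 5 years | Gap |
|---|---|---|---|---|---|
| 0.10 | 39.35 | 35.08 | 4.27 | 29.20 | 10.15 |
| 0.15 | 52.76 | 47.28 | 5.48 | 39.70 | 13.07 |
| 0.25 | 71.35 | 64.58 | 6.77 | 55.11 | 16.24 |

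**Gap over time (points, across the three values of h)**

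| Time | 5%/year | 50% at 5 years |
|---|---|---|
| 30 days | at most 0.01 | at most 0.01 |
| 1 year | 0.2–0.5 | 0.6–1.4 |
| 3 years | 1.8–3.4 | 4.5–8.5 |
| 5 years | 4.3–6.8 | 10.2–16.2 |

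**Effect on the interval.** Trials were simulated with independent exponential times and no censoring other than death and the 5-year end, 10,000 trials per cell. The table shows how often the planned log-log Greenwood 95% interval contains the true 5-year proportion re-hospitalized, for h = 0.10 / 0.15 / 0.25.

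| n | 5%/year | 50% at 5 years |
|---|---|---|
| 95 | 85.4 / 81.2 / 72.2% | 54.6 / 40.7 / 21.2% |
| 70 | 87.7 / 83.8 / 77.3% | 63.6 / 51.1 / 33.7% |

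A complementary log-log interval for the cumulative incidence covers it in 93.9 to 96.2% of trials in all 12 cells. The planned interval has a half-width of about 10 to 14 points at 5 years; it fails because it is centred on a different quantity.

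**With drop-out.** A separate simulation (n = 95, 4,000 runs, assumed drop-out hazard 0.03 per year) gave mean 5-year values of 39.3% against 35.0% for h = 0.10 with 5% mortality per year, and 63.2% against 48.2% for h = 0.20 with 50% mortality. Kaplan-Meier was at or above the cumulative incidence in every run.

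**The case against.** The best counter-argument is that this is one exploratory, descriptive endpoint with no test or pass criterion, and that the SAP names the estimator and states its censoring rule. Both interim analyses are triggered at 30-day follow-up, where the gap is negligible. That is correct, and it limits the importance of the point. It does not change what the final 5-year figure estimates.

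Second, the planned table gives numbers with events. If follow-up is complete except for death, events divided by subjects treated equals the cumulative incidence, so a careful reader could recover it. This holds only without drop-out. With h = 0.10, λ = 0.0513 and a drop-out hazard of 0.03, the expected crude proportion is 0.10/0.1813 × [1 − exp(−0.9065)] = 32.9%, below the true 35.1%. In either case the printed rate and interval stay as they are.

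Third, the sizes lean high. What matters is death without a prior re-hospitalization, and all-cause mortality overstates it if re-hospitalized subjects die sooner. This stands. Holding total 5-year mortality fixed and assuming the death hazard triples after re-hospitalization, the 5-year gap falls to 3.1–3.8 points (5% per year) or 8.0–10.0 points (50%). The 50% figure is also an upper bound from another protocol. At 5% per year the gap is smaller than the interval's half-width.

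Fourth, the Kaplan-Meier interval covers its own target about 95% of the time, so the coverage figures restate the difference in target and are not a separate defect. That is fair. They show what happens if the interval is read as the proportion of treated subjects affected.

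Finally, section 7.10 names no specific non-fatal time-to-event outcome, so the point applies there only if such outcomes are analysed.

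**Conclusion.** The concern holds. As written, the SAP will produce late figures for heart failure re-hospitalization that overstate the proportion of treated subjects with the event. The direction is a property of the estimator and depends on no assumed rate.

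The size is illustrative. Under independent constant hazards it is about 4 to 7 points at 5 years with 5% mortality per year and 10 to 16 points with 50% mortality at 5 years. If deaths concentrate after re-hospitalization, as in the tripled-hazard case, it is about 3 to 10 points across the two mortality scenarios. Up to 1 year it is small.

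The 30-day primary safety endpoint and unanticipated adverse device effects are reported as simple proportions and are not affected. The change should be made, but no decision rule in the study depends on it.

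**What to change.** In sections 7.2 and 7.9.3, and in 7.10 for any non-fatal outcome analysed as time-to-event, specify the Aalen-Johansen cumulative incidence with death as a competing event, with its 95% confidence interval, at the time points already planned. Keep Kaplan-Meier for all-cause death and, if wanted, for the composite of death or heart failure re-hospitalization. Retain the death-censored Kaplan-Meier figure only as a supplementary line, labelled as such, for comparison with publications that used it.

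The cost is SAP wording and a standard software option, with no new data. The drawback is having two figures to present and explain where published comparators used Kaplan-Meier.

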## 7.3 Center Pooling

Although data for this study will be collected from multiple centers, no center pooling analyses are planned.

## **7.4 Handling of Missing, Unused, and Spurious Data and Dropouts**

Every effort will be undertaken to minimize missing, unused, and spurious data and dropouts. In time-to-event outcomes, drop-outs will be censored at the time of discontinuation, consistent with the Kaplan-Meier approach.

Unless otherwise specified in each objective, no statistical techniques will be used to impute missing data for continuous or categorical outcomes. If a subject's data are missing for any reason, that subject will not be included in that portion of the analysis. The number of subjects included in each analysis will be reported so that the reader can assess the potential impact of missing data.

In the case of partial dates, if only the month and year are known, the event or assessment will be analyzed as if it occurred on the 15th of that month. If only the year is known, the event or assessment will be analyzed as if it occurred on June 30th of that year. These resolutions of partial dates are subject to the restrictions that events must occur no earlier than the procedure date or after study exit. For more complex imputations of dates, determination will be made on a case-by-case basis based on the most suitable date range.

## **7.5 Adjustments for Multiple Comparisons**

No adjustments for multiple comparisons are planned.

## **7.6 Demographic and Other Baseline Characteristics**

Demographics, hemodynamic measurements at screening, as well as medical history will be summarized using methods described in **Section 7.2** for the subjects in the Consented Subjects and Approved Subjects analysis sets.

## **7.7 Treatment Characteristics**

Treatment characteristics will be summarized using methods described in **Section 7.2** for the subjects in the Approved Subjects analysis set.

## **7.8 Interim Analyses**

Interim analyses are planned for publication when 50 subjects had the opportunity to be followed for 30 days and a second analysis for CE submission when 75 subjects had the opportunity to be followed for 30 days. The final analysis and report will be completed when all enrolled subjects have completed the 5-year follow-up.

## 7.9 Evaluation of Objectives

### 7.9.1 Primary Safety Endpoint

- Implant or delivery related SAEs (through 30 days post-procedure)

Hypothesis/Decision Criteria:

No specific hypotheses or pass/fail criteria have been set. The analysis will be descriptive and no statistical hypothesis tests are planned.

Endpoint Definition/Parameters to Be Estimated:

The severity and relationship of an AE to the implant and delivery are collected on the AE CRFs. AEs are coded using MedDRA coding. AE are reported by sites and may be reviewed and adjudicated by the CEC. An AE through 30 days post-procedure is one that occurs between day 0 (the date of index procedure) and the 30th day after the index procedure.

An implant or delivery related SAE is defined as follows.

If site AE CRF indicates the following:

- “Serious adverse event?” is answered “Yes”.
- “Relation to the TMVR device/procedure” is answered either “Possibly related”, “Probably related”, or “Definitely related”.

However, if the event was reviewed and adjudicated by the CEC, then the seriousness and relationship recorded by the CEC will be used instead.

Data Collection and Analysis Dataset:

Data will be collected on AE CRFs. Analysis will be performed on the Attempted Subjects analysis set.

Analysis Method:

The number of events, the number and proportion of subjects who have at least one SAE recorded as TMVR device/procedure related and its associated 95% exact confidence interval will be reported.

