### 6.1 Adverse Events & Definitions

**Adverse Event (AE):** Any untoward medical occurrence, unintended disease or injury, or untoward clinical signs (including abnormal laboratory findings) in subjects, users or other persons, whether or not related to the investigational medical device.

**Adverse Device Event (ADE):** Adverse event related to the use of an investigational medical device

**Serious Adverse Event (SAE):** Any adverse event that

- a) led to death,
- b) led to serious deterioration in the health of the subject, that either resulted in
  - 1) a life-threatening illness or injury, or
  - 2) a permanent impairment of a body structure or a body function, or
  - 3) in-patient or prolonged hospitalization, or
  - 4) medical or surgical intervention to prevent life-threatening illness or injury or permanent impairment to a body structure or a body function,
- c) led to foetal distress, foetal death or a congenital abnormality or birth defect

*NOTE: Planned hospitalisation for a pre-existing condition, or a procedure required by the CIP, without serious deterioration in health, is not considered a serious adverse event.*

**Serious Adverse Device Effects (SADE):** Adverse device effect that has resulted in any of the consequences characteristic of a Serious Adverse Event.

AEs or SAEs will also be classified as to their relationship to the Investigational Device, as follows:

**Not Related:** The event is due to an underlying or concurrent illness or effect of another device, drug or intervention and is not related to the investigational device or procedure.

**Remotely Related:** The event's relationship to the investigational device or procedure, cannot be completely ruled out, but is unlikely, and an alternative etiology is more likely.

**Possible:** The event has a strong temporal relationship to the investigational device or procedure, and an alternative etiology is equally or less likely.

**Probable:** The event has a strong temporal relationship to the use of the investigational device or procedure and another etiology is unlikely or significantly less likely.

**Definite:** The event can only be attributed to the use of the investigational device or procedure.

**Not Assessable:** The event's relationship to the use of the investigational device or procedure cannot be assessed.

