## 5.3 Clinical Events Committee and Data Safety Monitoring Board

The combined Clinical Events Committee (CEC) and Data Safety Monitoring Board (DSMB) will provide independent medical review and adjudication of adverse event data used in the safety assessment of the investigational device. The CEC will adjudicate all deaths, serious adverse events (SAEs), and safety endpoint events reported by the investigators. The CEC will follow the recommendations of the Mitral Valve Academic Research Consortium (MVARC) for classifying adverse events that relate to clinical safety endpoints.

A DSMB will assess interim study data and provide recommendations to Medtronic regarding study conduct, should they identify any issues that may affect the safety of the study subjects. The DSMB consists of a minimum of three members: 1) cardiologist with expertise in the management of mitral disease, 2) a cardiothoracic surgeon with expertise in mitral valve repair and replacement, and 3) a biostatistician. DSMB members are free from bias towards the study and independent from both the study and investigators and Medtronic.

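### Does the pilot SAP leave the primary safety rate open when an SAE's relationship is Not Assessable or missing, or when two sections name different analysis sets?

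*Combined protocol and SAP*

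**What the plan says.** The SAP in the file belongs to the transapical Pilot Study (CIP-1403), so that CIP is the one to read it against.

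- **Definition.** SAP 7.9.1 treats an SAE as implant or delivery related when the site form marks it serious and the relationship "is answered either “Possibly related”, “Probably related”, or “Definitely related". If the CEC has adjudicated the event, "then the seriousness and relationship recorded by the CEC will be used instead". The result is the number of events and the number and proportion of subjects with one or more qualifying SAEs through day 30, with an exact 95% interval, on the attempted set.
- **Scale.** CIP-1403 section 6.1 has six categories. One is Not Assessable: "The event's relationship to the use of the investigational device or procedure cannot be assessed". SAP 7.9.1 does not mention it.
- **Missing data.** SAP 7.4 imputes nothing unless an objective says otherwise, and adds: "If a subject's data are missing for any reason, that subject will not be included in that portion of the analysis". It also requires the number of subjects in each analysis to be reported.
- **Adjudication.** SAP 5.3: "The CEC will adjudicate all deaths, serious adverse events (SAEs), and safety endpoint events reported by the investigators". SAP 7.10 repeats it: "The CEC will adjudicate all deaths, SAEs, and safety endpoint events reported by the investigators".
- **Analysis sets.** SAP 7.1.3 has one sentence naming Approved Subjects for the primary analysis. Its next sentence leaves the set for each objective to that objective's section. Its Attempted Implant (Safety) bullet claims all safety data and the clinical outcomes, with MLHFQ among them. SAP 7.9.3 then summarises MLHFQ on Approved Subjects.
- **Other reporting.** Under SAP 7.10, "the safety data will be presented at aggregate and individual event levels as tables and listings", with a breakdown by causal relationship. Under SAP 7.2, "case summaries for all subjects will be provided to the FDA".

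**The concern.** The study's primary endpoint is a proportion, and two things about it appear unsettled.

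First, the numerator and denominator. An SAE whose final relationship is Not Assessable is not on the list in 7.9.1, and the section does not say so outright. An SAE whose relationship is still blank seems to fall under two rules. By the list it is not an event and the subject stays in the denominator. By 7.4, read literally, the subject leaves the analysis. Two programmers could report different denominators. Both readings give a rate no higher than counting the event as related, so any ambiguity works in the device's favour. Section 7.8 plans interim analyses for publication and for a CE submission, so the figure will be used.

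Second, the analysis set. A reader who stops at the primary-analysis sentence in 7.1.3 would use Approved Subjects. That set includes people who never entered the procedure room, which would dilute the rate.

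**Working it through.** **No plan figure to reproduce.** SAP section 6 gives 95 as a cap on treated subjects and says that the size was not statistically derived. No event rate, alpha or power is stated. The check therefore asks which rule applies, and how much the answer could move.

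**Step 1: which rule applies to each kind of SAE**

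| Final relationship | 7.9.1 | 7.4 | Result |
|---|---|---|---|
| Possible, probable, definite | on the list | not missing | event |
| Not related, remote | off the list | not missing | non-event |
| Not Assessable | off the list | a recorded value, so not missing | non-event, subject kept |
| Blank at site, CEC value present | CEC value used | not missing | as adjudicated |
| Blank after adjudication | not on the list | would drop the subject if read literally | the only open cell |

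The open cell needs an SAE that the CEC was required to adjudicate and for which it recorded no relationship. The CEC charter and the AE form are not among the documents, so whether that can happen cannot be seen.

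For that cell the literal reading of 7.4 is also strained. The endpoint asks whether a subject has at least one qualifying SAE. Applied strictly, 7.4 would remove a subject with a confirmed related SAE because a second SAE lacked a relationship, which no analyst would do. The natural reading is that the subject stays in.

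**Step 2: size of the numerator and denominator question**

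Let x be subjects with a related SAE and k be further subjects whose only candidate SAE is Not Assessable or blank. The options are:

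- non-event: x/N
- dropped (blank only): x/(N − k)
- counted as related: (x + k)/N

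Counting as related is the upper bound, because (x + k)(N − k) − xN = k(N − x − k) ≥ 0. One subject adds 1/N: 1/50 = 2.00 points, 1/75 = 1.33, 1/95 = 1.05.

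The values of x and k are assumed: a 20% rate, and k from 0 to 3. N = 50 is the first interim in 7.8 and N = 95 is the cap, both taken as the attempted denominator. Intervals are Clopper-Pearson 95%.

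| N | k | Non-event | Dropped | Related |
|---|---|---|---|---|
| 50 | 1 | 10/50 = 20.0% (10.0–33.7) | 10/49 = 20.4% (10.2–34.3) | 11/50 = 22.0% (11.5–36.0) |
| 50 | 3 | 10/50 = 20.0% (10.0–33.7) | 10/47 = 21.3% (10.7–35.7) | 13/50 = 26.0% (14.6–40.3) |
| 95 | 1 | 19/95 = 20.0% (12.5–29.5) | 19/94 = 20.2% (12.6–29.8) | 20/95 = 21.1% (13.4–30.6) |
| 95 | 3 | 19/95 = 20.0% (12.5–29.5) | 19/92 = 20.7% (12.9–30.4) | 22/95 = 23.2% (15.1–32.9) |

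The true ambiguity is between the first two result columns: at most 1.3 points at N = 50 and 0.7 at N = 95 for k = 3. The third column is a different definition, not a reading of the SAP. At k = 0 all three columns agree.

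**Step 3: the analysis set**

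Three statements bear on it. The primary-analysis sentence in 7.1.3 says Approved. The Attempted Implant (Safety) bullet in 7.1.3 says attempted for safety data. Section 7.9.1 says attempted. The deferral sentence in 7.1.3 gives precedence to 7.9.1, so attempted governs.

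If the stray sentence were followed, with an assumed 3 to 10 approved subjects never attempted and free of events, 19/95 = 20.0% would become 19/98 = 19.4% to 19/105 = 18.1%.

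**Step 4: MLHFQ**

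Here the deferral sentence points to Approved (7.9.3), while the set definition lists MLHFQ under attempted. The attempted set is a subset of Approved, the CIP-1403 summary schedules follow-up for treated subjects, and 7.9.3 computes change on paired data only. An approved but untreated subject has a baseline score and essentially no 12-month score. Paired change is therefore essentially the same under either set, and only the baseline summary could move.

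**The case for a change.** The strongest case for a change is that this is the primary endpoint and its rule for unclassified SAEs has to be inferred. The SAP spells out numerator and denominator for the exploratory MVARC composites but not here. Section 7.9.1 says that AEs may be adjudicated, which sits awkwardly with adjudication of all SAEs. Few unclassified cases is not the same as none. A denominator sentence and a sensitivity line counting such SAEs as related would cost little and leave the planned rate intact.

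Part of this stands. Section 7.9.1 does not expressly set 7.4 aside, and one sentence saying that all attempted subjects stay in the denominator would close the open cell.

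The rest carries less weight:

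- The may in 7.9.1 refers to AEs in general. Sections 5.3 and 7.10 cover SAEs specifically, so the two are compatible.
- The MVARC composites need an explicit denominator because they rely on echo, walk-test and questionnaire results that are often missing at a visit. A count of adjudicated events has no such dependence.
- Any effect of the rule would show. Section 7.10 breaks safety data down by causal relationship and presents individual events, 7.4 reports the number of subjects analysed, and case summaries go to the FDA. None of these is a dedicated 30-day reclassified rate, but a reader can see how many SAEs fell outside the three categories.
- A sensitivity line for a descriptive endpoint with no success criterion is a preference. It would also count some SAEs that are truly unrelated.

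**Conclusion.** No change to the plan follows. Not Assessable is settled by the closed list in 7.9.1. A blank relationship matters only if it survives CEC adjudication of every SAE, and a sensible analyst would then keep the subject in the denominator. In the illustration (20% rate, three subjects) the two readings differ by 1.3 points at N = 50 and 0.7 at N = 95, well within exact intervals about 24 and 17 points wide. Even counting such SAEs as related gives 26.0% and 23.2%, inside the base intervals of 10.0–33.7% and 12.5–29.5%. The rate and the count of unclassified subjects are assumptions; with none, nothing moves.

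The conflict in 7.1.3 is a clerical slip. The version history records that Approved was replaced by Attempted for various outcomes, so the primary-analysis sentence is probably a leftover, though that is an inference. Attempted governs the primary endpoint. The two names for that set and the two MLHFQ assignments are also editorial and can be reconciled whenever the SAP is next revised; paired MLHFQ change is essentially unaffected.

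This view rests on the CEC adjudicating all SAEs as 5.3 and 7.10 state. If many SAEs were left without an adjudicated relationship, the denominator would need an explicit rule.
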